8.1.9 Week 48 or Early Termination (± 7 days)

Every effort should be made to conduct the Week 48 visit and maintain the +/- 7 day window. However, due to concerns related to the COVID-19 pandemic, the Week 48 visit window may be modified beyond the +/- 7 day window, in order to minimize any potential risks to study participant safety and to comply with governmental and local institutional guidance (e.g., study site has a policy that a clinical research visit must be delayed). Under these circumstances, the visit window may be extended (up to a maximum treatment duration of 60 weeks), but every attempt should be made to conduct the visit as close to the date the visit is due as possible. If the visit window is modified, participants should be evaluated remotely (e.g., via phone) at the time of the scheduled Week 48 visit to perform and document appropriate safety assessments. Study medication may be sent to the participant via tracked courier. For any such cases, the investigator should discuss the specific circumstances of each case with the sponsor medical monitor (or designee) who must approve the request prior to any modification of the visit window.

Sponsor Medical Monitor

All participants returning for week 48 will undergo the following procedures:

- Physical exam
- Vital signs (sitting blood pressure, pulse, temperature, respiration rate)
- Weight
- Documentation of concomitant treatment
- Documentation of adverse events
- Blood samples for:
 - Safety laboratory tests (hematology and serum chemistry, as listed in Section 8.2)
 - Pharmacokinetics* (in plasma)
 - Biomarker/banking
- Urinalysis (see Section 8.2)
- Resting 12-lead ECG
- Lumbar puncture* (± 14 days of week 48)
- Post lumbar puncture safety telephone follow-up (1 to 3 days after lumbar puncture)
- Sheehan Suicidality Tracking Scale
- ADAS-Cog 11
- CDR-SOB
- Volumetric MRI (± 14 days of week 48)
- NPI
- ADCS-ADL
- Neuropsychological Test Battery
 - Craft Story 21 (Immediate and Delayed)
 - Benson Complex Figure
 - Multilingual Naming Test (MINT)
 - Letter & Category Fluency
 - Trail Making Test A&B
 - Number Span Test
- MMSE
- Montreal Cognitive Assessment (MoCA)
- Research Satisfaction Survey

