#### 4.8.3 Analysis of the Co-Primary Outcome Measures

The primary analyses use the within-participant change in ADAS-Cog 11 and in CDR-SOB as the outcome in two separate similar mixed effects repeated measures models, including all available in-clinic outcomes during the double blind phase in the mITT population. Fixed effects in the models are APOE status (e4 carrier vs e4 noncarrier), MMSE (mild vs. moderate) status, site, baseline ADAS-Cog or CDR-SOB score, respectively, treatment group (active vs placebo), visit, visit x baseline score interaction, and visit x treatment group interaction. Visit is treated as a categorical variable. Sites with only one subject will be pooled together. Descriptive statistics showing the timing of the primary outcome assessment will be presented by treatment arm as well as break-outs by baseline characteristics (e.g. APOE status, Mild/Moderate status based on MMSE, age group, and sex).

A random effect will be included for participant. The within-participant covariance will be unstructured. If the model does not converge, MMSE status will be removed from the model. If the model still does not converge, the following structures for the within-subject covariance will be fit, sequentially, until the structure is found that results in convergence of the model: Huynh-Feldt, Toeplitz, Autoregressive (1), and Compound Symmetry. Error degrees of freedom will be calculated using the Kenward-Roger approximation if an unstructured covariance is used; otherwise, a sandwich estimator will be utilized to estimate the covariance structure and degrees of freedom will be calculated using the between-within method. For the ADAS-Cog 11and CDR-SOB, each primary endpoint will be tested using model-adjusted least squares means at the week 48 visit. Point estimates, standard errors, two-sided 95% confidence intervals, and p-values will be presented.

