K=20, or in a similar manner in R. The outcome variable will be imputed in a monotone sequential manner.

- 2. Investigation of the impact of COVID-19 will be conducted by the following separate analyses:
  - i) A fixed effect to indicate an assessment occurring after March 13 (during the COVID pandemic) will be added to the model ("COVID indicator"), as well as the interaction of the COVID indicator x time. If the model with the interaction term fails to converge, the interaction term will be omitted.
  - A fixed effect to indicate the timing of the Week 48 assessment will be included in the primary analysis model. The fixed effect will be subject-based and include 2 levels. The subjects either discontinuing early or completing their in-clinic assessment within the originally specified week 48 window (Days 323-372) will be in one level of the effect and subjects with their week 48 assessment in the expanded portion of the window (days 373-420) in the another level.
  - iii) Remote assessments will be included in the model, with the model as specified for the primary analysis.
  - iv) Remote assessments will be included in the model, with the model as specified for the sensitivity analysis which includes the COVID indicator.

Additional supplemental analyses will run the primary model for each of the co-primaries but only include in-clinic "on-treatment" assessments (i.e. done within 3 days of the final dose of double-blind medication – see Section 4.3). These analysis will assess a more hypothetical estimand which focus on the effect of the study medication as intended.

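### The Week 48 timing sensitivity analysis (SAP 4.8.3, item 2(ii)) spreads a Week-48-only delay effect over all visits, so it recovers and corrects only part of it

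*SAP*

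**What the plan says.** SAP 4.8.3 lists four separate analyses of the impact of COVID-19 on the co-primary endpoints. The second, item 2(ii), reads: "A fixed effect to indicate the timing of the Week 48 assessment will be included in the primary analysis model". Its form is given as "The fixed effect will be subject-based and include 2 levels". Early discontinuers, and subjects whose in-clinic assessment fell "within the originally specified week 48 window (Days 323-372) will be in one level of the effect", are set against "subjects with their week 48 assessment in the expanded portion of the window (days 373-420) in the another level".

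The model that receives this term uses all in-clinic visits (Weeks 12, 24, 36 and 48). Its stated interactions are "visit x baseline score interaction, and visit x treatment group interaction", and "each primary endpoint will be tested using model-adjusted least squares means at the week 48 visit". Item 2(i), directly above, adds a COVID indicator "as well as the interaction of the COVID indicator x time". Item 2(ii) states no comparable interaction.

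SAP Table 1 sets the Week 48 analysis window for ADAS-Cog and CDR at Days 295-420. Protocol 8.1.9 asks sites to "maintain the +/- 7 day window", but allows a COVID-related extension up to 60 weeks of treatment.

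**The concern.** The item is meant to show whether lengthening the Week 48 window matters. Delay acts at one visit: the Week 12, 24 and 36 scores were recorded before any Week 48 delay could occur. A subject-level constant without a visit interaction must fit all four visits together, so the three unaffected visits pull its estimate towards zero. Because treatment is compared at Week 48 only, the adjustment also falls short where it is needed and adds a small spurious adjustment at the earlier visits. A reader who took the fitted term, or a nearly unchanged treatment estimate, as evidence that delay is harmless would be relying on a diluted quantity.

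A second, lesser matter is that the two levels do not cover everyone with a place in the Week 48 analysis, and some subjects could fit both.

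**Working it through.** **Window coverage.** The Table 1 window reproduces: the midpoint of Days 252 and 336 is (252 + 336)/2 = 294, so Week 48 starts on Day 295, and 60 x 7 = 420. That is 126 days. Level 1 covers Days 323-372 (50 days) and level 2 covers Days 373-420 (48 days), together 98. Days 295-322 remain: 28 of 126 days, or 22%.

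**Recovery of a Week-48-only effect.** Let the true delay effect be d at Week 48 and 0 at Weeks 12, 24 and 36. With visit and visit x treatment in the model, the arm-by-visit means are free. The timing coefficient is therefore the generalised least squares fit of a constant to the within-arm late-minus-other differences (0, 0, 0, d). It equals w x d, where w = (1'S^-1)_4 / (1'S^-1 1) and S is the 4 x 4 within-subject covariance. This takes complete data and ignores the other covariates. The documents give an SD of 6 for ADAS-Cog change at 6 and 12 months. The SDs at Weeks 12 and 36 and the between-visit correlations are assumptions.

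| Assumed covariance | w |
|---|---|
| SD 6 throughout, compound symmetry | 1/4 = 0.25 |
| SD 6 throughout, AR(1), correlation 0.4 / 0.6 / 0.8 | 1/(4 - 2 x correlation) = 0.31 / 0.36 / 0.42 |
| Week 12 SD 5, others 6, either structure, correlation 0.4-0.8 | 0.04 to 0.33 |
| Week 12 SD 4, others 6, either structure, correlation 0.4-0.8 | -0.12 to 0.23 |

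**Effect on the treatment contrast.** With late proportions p1 and p0 in the two arms:
- Week 48 shift without adjustment: (p1 - p0) x d
- Week 48 shift left after item 2(ii): (p1 - p0) x d x (1 - w)
- Spurious shift at Weeks 12, 24 and 36: -(p1 - p0) x d x w
- Week 48 shift left with a timing x visit term: 0

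If p1 = p0, all of these are zero.

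**Size on ADAS-Cog.** The documents cite a placebo decline of 3.9 points over 12 months, treated here as 48 weeks.
- Longest delay: (420 - 336)/7 = 12 weeks, so d = 3.9/48 x 12 = 0.975. Over 52 weeks it would be 3.9/52 x 12 = 0.90.
- Midpoint of level 2: (396.5 - 336)/7 = 8.6 weeks, so d = 3.9/48 x 8.6 = 0.70.
- Assumed imbalance of 15 percentage points (for example 40% against 25%): 0.15 x 0.70 = 0.105 to 0.15 x 0.975 = 0.146 before adjustment.
- Left under compound symmetry: 0.75 x 0.105 = 0.08 to 0.75 x 0.146 = 0.11.
- Assumed 10% against 30% late, 12-week delay, Week 12 SD 5: 0.20 x 0.975 = 0.195 before adjustment, and 0.13-0.19 after it.

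**Size on CDR-SOB**, from the cited decline of 1.6 points, with the same 15-point imbalance and compound symmetry: the delay is worth 1.6/48 x 8.6 = 0.29 to 1.6/48 x 12 = 0.40. The shift is 0.15 x 0.29 = 0.043 to 0.15 x 0.40 = 0.060, and 0.75 x 0.043 = 0.03 to 0.75 x 0.060 = 0.045 remains.

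**For scale.** A residual of 0.11 is 0.11/2.64 = 4% of the design difference on ADAS-Cog. The standard error of that difference with 124 per arm is 6 x sqrt(2/124) = 0.76, so 0.11 is about 0.14 standard errors.

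**The case against.** The case for leaving the item alone has several parts, and some of it stands.

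- **Nothing primary depends on it.** This stands. It is one supportive analysis, and balanced delay leaves the treatment contrast unchanged. Blinding, randomization stratified by site and site in the model all make a large imbalance less likely. The 15- and 20-point imbalances are illustrations, not expectations.
- **Timing is examined elsewhere.** This stands in part. SAP 4.8.3 also plans descriptive statistics on assessment timing by arm, which would reveal an imbalance, but they do not adjust for one. Item 2(i) follows calendar date, so on-time and late visits during the pandemic carry the same indicator.
- **A subject-level term may be meant to absorb stable differences between late and other subjects.** It would do that, but the SAP describes the term as representing the timing of the Week 48 assessment, and a constant across visits represents that poorly.
- **The gap in the levels is nearly empty.** Largely accepted. The COVID provision only moves visits later, and the protocol visit window opens on Day 336 - 7 = Day 329. Early-termination visits on Days 295-322 belong to level 1. Remote visits are allowed only for visits other than Week 48 (Protocol 8.1), so completers without an in-clinic Week 48 record should be rare.

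A reader might infer three stronger things that the documents do not support:
- That Days 323-372 is the wrong window because the protocol allows only 7 days either side. SAP 4.3.8 separates visit windows from analysis windows, and the SAP revision history says version 2.0 expanded the Week 48 analysis window. The range may be the analysis window of version 1.0, which is not among the documents.
- That unclassified subjects are lost from the model at every visit. That is how software commonly treats a missing class value; the SAP states no such rule.
- That the SAP will cite the timing coefficient as proof that delay is harmless. It does not say how the term will be reported.

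**Conclusion.** The concern holds as a fault in the specification of a supportive analysis. As written, item 2(ii) recovers roughly a quarter to two-fifths of a Week-48-only delay effect under equal variances, and less under some unequal-variance structures. With unbalanced delay, most of the shift in the Week 48 contrast remains. To say that the analysis cannot test timing at all would be too strong: it captures a share that depends on the covariance.

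The likely consequence is small: about 0.08-0.11 ADAS-Cog points left uncorrected, given delays of 8.6-12 weeks, linear decline at the cited placebo rate, a 15-point imbalance and compound symmetry. The planned covariance is unstructured, so the recovered share cannot be known in advance. The omission of Days 295-322 and of completers without an in-clinic Week 48 record is real but secondary. The primary test of both co-primary endpoints is unaffected.

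**What to change.** Reword item 2(ii) in the SAP:

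1. Make the timing term specific to Week 48. Either add timing x visit, or apply days late (or a late indicator) to the Week 48 record only, with the value 0 at Weeks 12, 24 and 36.
2. Define exhaustive, mutually exclusive levels over Days 295-420, and set the term to 0 when a subject has no Week 48 record. State whether discontinuing early refers to drug or study: Protocol section 10 encourages subjects who stop drug to continue visits, so one seen on Days 373-420 could now fit both levels.
3. To check whether the treatment effect differs in delayed subjects, add treatment x timing at Week 48. Neither the present term nor step 1 alone can show this.

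The cost is SAP wording and a changed covariate; no new data are needed. Precision will be limited in any form. With 248 analysed and an assumed 20% late, the standard error of the late-against-other contrast at Week 48 is about 6 x sqrt(1/49.6 + 1/198.4) = 0.95 points, as large as the delay effect itself. Report the estimate with its confidence interval, and do not read a non-significant term as showing no effect.

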#### Subgroup Analyses

Except where indicated, descriptive statistics for the two co-primary endpoints ADAS-Cog 11 score and CDR-SOB score, and their change from baseline, will be tabulated by visit, separately, for the subgroups defined by:

- o Sex
- Mild vs Moderate MMSE status
- APOE e4 status
- Participation during Covid-19 (opportunity to complete randomization phase before March 13, 2020 vs on or after March 13, 2020)

As a further exploratory analysis, for Mild vs Moderate MMSE baseline status subgroups an MMRM analysis will be utilized on each subgroup using the model specification as described above.

In addition, descriptive statistics will also be presented by visit in the Open Label Extension Phase, by original randomized group (BHV-4157 and Placebo to BHV4157).

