8.5 Genotyping

ApoE (e4 +/-) genotype is associated with the risk and age of onset of AD. ApoE genotyping will be performed at screening. The blood collection will total approximately 10 mL. Results of ApoE genotyping will be used in exploratory subgroup analyses to explore the relationship between ApoE genotype clinical course and response to treatment.

If a participant has agreed to allow his/her sample to be banked, then the DNA sample will be stored at the UCSD and used for additional genetic testing. Samples will be de-identified prior to being shared with outside investigators to preserve the confidentiality of participants. Participants can request in writing any time to have their samples destroyed. Results of this testing are for research purposes only and will not be disclosed to the participant or study partner.

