12.5 Analysis of Exploratory Endpoints

The exploratory endpoints include: (1) change in MoCA scores from baseline to week 48; (2) change in ADCOMS total score from baseline to week 48; (3) bilateral lateral ventricles and whole brain volume as measured by volumetric MRI; (4) a cognitive composite outcome computed using measures from the NACC Neuropsychological Test Battery (Craft Story 21 Recall (Immediate & Delayed), Benson Figure (Copy & Delayed Recall), Multilingual Naming Test (MINT), Letter & Category Fluency, Trail Making Test A & B, Number Span Forward & Backward; (5) BHV-4157 pharmacokinetics; (6) treatment response by Apo E genotype; and (7) CSF, serum and plasma biomarker panel (AB42, AB42/40 ratio, total tau, p-tau-181, neurogranin, NfL, YKL-40, VILIP, SNAP-25, sTREM2, GFAP) at week 24 and week 48. CSF will be assessed in a subset of the study population (estimated n=50 active, n=50 placebo). Their analyses are included in the SAP.

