#### 1.2.3 Exploratory Objectives

- To evaluate the efficacy of BHV-4157 as assessed by the Montreal Cognitive Assessment (MoCA)
- To evaluate the efficacy of BHV-4157 on performance using the AD Composite Score (ADCOMS)
- To evaluate volumetric MRI (bilateral lateral ventricles and whole brain volume)
- To evaluate the efficacy of BHV-4157 on performance on a cognitive composite outcome computed using measures from the NACC Neuropsychological Test Battery [Craft Story 21 Recall (Immediate & Delayed); Benson Complex Figure (Copy & Delayed Recall); Multilingual Naming Test; Letter & Category Fluency; Trail Making Test A & B; Number Span Forward and Backward]
- To analyze the pharmacokinetics of BHV-4157 and riluzole in plasma
- To evaluate treatment response by Apo E genotype
- To assess CSF, serum and plasma biomarkers (AB42, AB42/40 ratio, total tau, p-tau-181, neurogranin, NfL, YKL-40, VILIP, SNAP-25, sTREM2, GFAP) at screening, week 24 and week 48 of the double-blind phase. CSF will be assessed in a subset of the study population (estimated n=50 active, n=50 placebo)

Exploratory Open-Label Extension Phase objective is to evaluate the safety and tolerability of BHV-4157 as measured by the change in safety and tolerability measures including: (1) adverse events; (2) clinical laboratory tests; (3) vital signs; (4) physical examinations; (5) ECGs. Additional exploratory endpoint of evaluating long-term effects on clinical outcome measures.

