#### 2.4.3 Exploratory Endpoints

The following will be assessed during the double-blind phase :

- Efficacy of BHV-4157 assessed by the within-participant changes from baseline to week 48, compared between the treatment group and the placebo group, on Montreal Cognitive Assessment (MoCA) scores
- Efficacy of BHV-4157 assessed by the within-participant changes from baseline to week 48, compared between the treatment group and the placebo group, on performance using the AD Composite Score (ADCOMS), a composite outcome computed using 4 ADAS-Cog subscale items, 2 MMSE items, and the CDR Sum of Boxes (Wang et al., 2016)
- Efficacy of BHV-4157 assessed by the within-participant changes from baseline to week 48, compared between the treatment group and the placebo group, on volumetric MRI (bilateral lateral ventricles and whole brain volume)
- Efficacy of BHV-4157 assessed by the within-participant changes from baseline to week 48, compared between the treatment group and the placebo group, on a cognitive composite outcome computed using measures from the NACC Neuropsychological Test Battery [Craft Story 21 Recall (Immediate & Delayed); Benson Complex Figure (Copy & Delayed Recall); Multilingual Naming Test; Letter & Category Fluency; Trail Making Test A & B; Number Span Forward and Backward]
- Pharmacokinetics of BHV-4157 and riluzole in plasma
- Treatment response by APOE genotype
- CSF, serum and plasma biomarker panel (AB42, AB42/40 ratio, total tau, p-tau-181, neurogranin, NfL, YKL-40, VILIP, SNAP-25, sTREM2, GFAP) will be assessed at screening, week 24, and week 48. CSF will be assessed in a subset of the study population (estimated n=50 active, n=50 placebo)
- Open Label Exploratory Endpoints The change in safety and tolerability measures including: (1) adverse events; (2) clinical laboratory tests; (3) vital signs; (4) physical examinations; (5)

ECGs. Additional exploratory endpoint of evaluating long-term effects on clinical outcome measures.

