#### 4.3.5 Subpopulations

The subgroups of interest for this study are:

- Sex
- APOE (e4 vs no or missing)
- Mild vs moderate (mild AD:MMSE 20 to 24; moderate AD: MMSE 14 to 19)
- Participation during Covid-19 (opportunity to complete randomization phase before March 13, 2020 vs on or after March 13, 2020)

Except where indicated otherwise, descriptive summaries will be provided for the co-primary endpoints for each subgroup.

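### The SAP plans no estimate of treatment effect by ApoE genotype for its own exploratory objective, and counts unknown genotypes as non-carriers

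*SAP*

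**What the plan says.** The objective appears in both documents. SAP 1.2.3 has "To evaluate treatment response by Apo E genotype" among the exploratory objectives, and SAP 2.4.3 lists "Treatment response by APOE genotype" as an exploratory endpoint; Protocol 3.3 and 4.3 match. Protocol 8.5 states the purpose: "Results of ApoE genotyping will be used in exploratory subgroup analyses to explore the relationship between ApoE genotype clinical course and response to treatment". Protocol 12.5 names it as item (6) of the exploratory endpoints and hands over the method: "Their analyses are included in the SAP".

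What the SAP then provides:

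- SAP 4.8.5 has analysis text for MoCA, the neuropsychological composite, ADCOMS and the biomarker panel, but no entry for ApoE response.
- SAP 4.3.5 defines the subgroup as "APOE (e4 vs no or missing") and sets the default: "Except where indicated otherwise, descriptive summaries will be provided for the co-primary endpoints for each subgroup".
- SAP 4.8.3, Subgroup Analyses, repeats this for e4 status: "descriptive statistics for the two co-primary endpoints ADAS-Cog 11 score and CDR-SOB score, and their change from baseline, will be tabulated by visit".
- In that same subsection, "for Mild vs Moderate MMSE baseline status subgroups an MMRM analysis will be utilized on each subgroup". No such model is given for APOE.
- SAP 4.3.1.2 says what a continuous summary contains (n, mean, SD, median and range, given as examples) and that tables are split by randomized arm. SAP 4.3.7 bases efficacy analyses on observed data.
- In the primary model (SAP 4.3.3 and 4.8.3) APOE is a two-level main effect, carrier or non-carrier, with no treatment interaction and no stated level for a missing genotype.

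**The concern.** Response to treatment by genotype is a question about a treatment effect within each genotype group and about the difference between those effects. The plan specifies neither, and no interval for either. The APOE term in the primary model adjusts for prognosis and carries no information on differential response.

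Two features of the plan make the gap more visible. MMSE severity, whose subgroup response is not a listed objective, gets an MMRM in each stratum, while APOE, which is a listed objective, gets none. And unknown genotypes are placed with the non-carriers, so any carriers among them pull the two groups together.

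What is at stake is modest. Subgroup means printed without a difference or an interval invite over-reading, because nothing on the page shows how imprecise the comparison is.

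**Working it through.** **1. What the planned tables can yield.** With n, mean and SD by arm, visit and e4 status, a reader can form a crude effect in each genotype group (active mean minus placebo mean), its SE, and the carrier minus non-carrier contrast. That contrast is unadjusted, and at Week 48 it uses only people observed at Week 48. The primary MMRM adjusts for baseline score, MMSE status and site, and uses earlier visits of those who drop out, under MAR (SAP 4.3.1.1).

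**2. The plan's own figures (SAP 4.2, Protocol 12.1.1).** Inputs: 124 per arm after 26% dropout, two-sided 5%; ADAS-Cog difference 2.64, SD 6; CDR-SOB difference 0.95, SD 2.3; correlation 0.45; interim pass probability 0.937. Normal approximation:

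- ADAS-Cog: SE = 6 × √(2/124) = 0.762; 2.64/0.762 = 3.465; power = Φ(3.465 − 1.96) = 0.934 (stated 0.92).
- CDR-SOB: SE = 2.3 × √(2/124) = 0.292; 0.95/0.292 = 3.25; power = 0.902 (stated 0.90).
- Joint power at correlation 0.45 is 0.857; × 0.937 = 0.803 (stated 0.80).

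The stated figures reproduce closely. The documents give no precision figure for the APOE question.

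**3. Precision of the APOE contrast.** The carrier share is not in the documents; 40 to 70% is assumed. With n_c carriers and n_n non-carriers per arm out of 124, SE = SD × √(2/n_c + 2/n_n). For example, at 60% carriers, rounded to 74 and 50: √(36 × (2/74 + 2/50)) = 1.55, and 1.96 × 1.55 = 3.04. The table uses unrounded counts.

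| Carrier share | n per arm (carrier / non-carrier) | ADAS-Cog 95% half-width | CDR-SOB 95% half-width | Power if the interaction is 2.64 ADAS-Cog | Power if it is 0.95 CDR-SOB |
|---|---|---|---|---|---|
| 40% | 49.6 / 74.4 | 3.05 | 1.17 | 0.40 | 0.36 |
| 50% | 62 / 62 | 2.99 | 1.15 | 0.41 | 0.37 |
| 60% | 74.4 / 49.6 | 3.05 | 1.17 | 0.40 | 0.36 |
| 70% | 86.8 / 37.2 | 3.26 | 1.25 | 0.36 | 0.32 |

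The interaction detectable with 80% power is (1.96 + 0.8416) × SE, which is 4.3 to 4.7 ADAS-Cog points or 1.6 to 1.8 CDR-SOB points.

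**4. Dilution from pooling unknown genotypes.** Let m be the missing share and p the carrier share, with missingness unrelated to genotype. True carriers then make up mp / [(1 − p)(1 − m) + m] of the pooled group. Neither share is in the documents. For p from 50 to 70%:

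- m = 1%: 1.0 to 2.3%
- m = 5%: 4.8 to 10.4% (at p = 50%: 0.025/0.525 = 4.8%)
- m = 10%: 9.1 to 18.9%

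The carrier versus non-carrier contrast shrinks by about that fraction.

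**The case against.** The strongest reply is that descriptive tables suit an objective of this rank. It is one of seven exploratory items, Protocol 8.5 promises only exploration, and SAP 4.3.4 treats any tested exploratory endpoint as descriptive. The primary estimand concerns the whole mITT population and does not bind a subgroup table. MMSE severity is a randomization stratum and APOE is not, which is a plausible reason to model one and not the other. The MMSE analysis is also only a separate model per stratum, so it is no precedent for an interaction contrast. ApoE is drawn from everyone at screening, so the missing share may well be small, and the SAP revision history shows that its handling in the subgroup definition was set deliberately. Finally, the interval would be wider than the whole assumed effect on either side, so the model would rarely support a claim.

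Much of this stands, and it rules out stronger readings. A reader might infer that the objective cannot be answered at all, or that nothing could be said about differential response. The documents do not support that, because the tables are by arm and allow a crude contrast. A reader might also call the tables completer means. They are observed-case summaries by visit: dropouts count at each visit they attended, participants off drug may continue visits (Protocol section 10), and an assessment from Day 295 falls in the Week 48 window (SAP Table 1). The 26% dropout is a planning ceiling.

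What the reply does not remove is that the protocol sends this analysis to the SAP and the SAP specifies no effect estimate or interval. Low precision is a reason to print the interval.

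**Conclusion.** The point holds as a minor gap in an exploratory analysis. The SAP plans no treatment effect by genotype, no confidence interval and no carrier versus non-carrier contrast for this objective, and its subgroup rule places unknown genotypes with non-carriers.

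The size is limited. A proper estimate would carry a 95% half-width of about 3.0 to 3.3 ADAS-Cog points and 1.15 to 1.25 CDR-SOB points, against assumed overall effects of 2.64 and 0.95. These figures rest on 40 to 70% carriers, 124 per arm observed at Week 48, the planning SDs, and a two-sample approximation without covariate adjustment. Pooling unknowns weakens the contrast but does not defeat it unless the missing share is large. No power figure and no primary conclusion is affected.

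**What to change.** Add to the SAP one exploratory model per co-primary endpoint: the primary MMRM plus treatment × APOE, visit × APOE and treatment × visit × APOE. Report the Week 48 treatment effect in carriers, the effect in non-carriers, and their difference, each with a 95% CI.

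Leave participants of unknown genotype out of the contrast, or show them as their own level. State one rule for missing genotype and apply it to both the subgroup definition and the APOE term in the primary model, where none is given now.

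Label the result exploratory and imprecise, with the expected half-widths stated in advance. The cost is two further models on data already collected. The drawback is that the intervals will be wide, so the output is an estimate with its uncertainty and not a powered test.
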